- Study Duration** Excluding the Screening Period (approximately 28 days in duration) and Ivacaftor Run-in Period (approximately 4 weeks in duration), subjects who complete the Active Comparator Treatment Period (including those who prematurely discontinue study treatment) will participate in this study for up to 13 weeks. During the Active Comparator Treatment Period, study drug (VX-661/ivacaftor or ivacaftor only) will be administered up to 8 weeks. A Safety Follow-up Visit will occur 28 days ± 7 days after the final dose of study drug. A Safety Follow-Up Visit is not required for subjects who have completed the Week 8 Visit and have enrolled in the extension study of VX-661 in combination with ivacaftor within 28 days after the last dose of study drug.
- Study Design** This is a Phase 3, randomized, double-blind, ivacaftor-controlled, parallel-group, multicenter study in subjects aged 12 years and older with CF who are heterozygous for the *F508del-CFTR* mutation and a second *CFTR* allele with a gating defect that is clinically demonstrated to be ivacaftor responsive. This study includes the following:
- Screening Period (Week -8 to Week -4)
  - Ivacaftor Run-in Period where all subjects will receive ivacaftor (Week -4 to Day -1)
  - Active Comparator Treatment Period (Day 1 through Week 8 ± 5 days)
  - Safety Follow-up Visit (28 days ± 7 days after the final dose of study drug)

Subjects will be stratified by age at the Screening Visit (<18 versus ≥18 years of age), type of mutation on the second *CFTR* allele (*R117H* versus other allowed mutations), and percent predicted FEV1 severity determined at the end of the Ivacaftor Run-in Period (<70 versus ≥70) and then randomized (1:1) to 1 of the following 2 treatment arms:

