j All standard digital ECGs will be performed before dosing and after the subject has been supine for at least 5 minutes. At the Day 1 and Week 2 Visits, ECGs will be collected before dosing and at 1.5, 3, 4, and 6 hours after the morning dose. The ECG will be performed before the morning dose of study drug at Week -4, Week -2, and Week 4. Single ECGs will be performed at Week 8, ETT, and Safety Follow-up Visits. ECGs collected on Week -4 and Day 1 before dosing will be performed in triplicate. Where repeats of the same assessment are required at a given visit, if study drug is not administered on the day of the visit (i.e., study drug interruption or permanent discontinuation of study drug), only 1 ECG will be collected.

k Vital signs and pulse oximetry will be collected before dosing after the subject has been at rest (seated or supine) for at least 5 minutes.

l At all visits, spirometry will be performed for all subjects pre-bronchodilator and before dosing (Section 11.6.1). On Days 1 and 15, subjects <18 years of age at the Screening Visit will have additional spirometry assessments performed at 2 and 4 hours postdose. If more than 1 spirometry assessment is required at a visit, bronchodilators will be withheld until the last scheduled spirometry assessment is completed.

m The sweat chloride collection on dosing days should occur before the morning dose of the study drugs. At each time point, 2 samples will be collected, 1 from each arm (left and right). Collection of sweat chloride will not overlap with any other study assessments.

n Blood samples will be collected before the first dose of study drug.

o Subjects will require 4 hours of fasting before the blood sample for the lipid panel is obtained.

**Table 3-2 Ivacaftor Run-in Period, Active Comparator Treatment Period, ETT, and Safety Follow-up Visit Assessments – Study VX14-661-109**

Event/Assessment a	Ivacaftor Run-in Period b		Active Comparator Treatment Period				ETT Visit c	Safety Follow-up Visit 28 days (± 7 Days) After Last Dose d
	Week -4 (Day -28 ± 2 Days)	Week -2 (Day -14) (± 2 Days)	Day 1	Week 2 (Day 15) (± 2 Days)	Week 4 (Day 29) (± 5 Days)	Week 8 (Day 57) (± 5 Days)		
Vitamin levels			X			X	X	X
PK sampling p		X		X			X	X
Randomization f			X					
Meal(s) or snack(s) at site g	X	X	X	X	X			
Ivacaftor dosing i	X							

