### 11.7.7 Liver Function Test Parameters

#### Liver Function Testing

Liver function testing (ALT, AST, GGT, ALP, direct bilirubin, and total bilirubin) must be performed as noted in [Table 3-2](#) for serum chemistry, while subjects are receiving study drug treatment and at the Safety Follow-up Visit. These blood samples should be processed and shipped immediately per the Laboratory Manual.

Subjects with new treatment-emergent ALT or AST elevations of  $>3 \times \text{ULN}$  and clinical symptoms must be followed closely, including repeat confirmatory testing performed by the central laboratory within 48 to 72 hours of the initial finding and subsequent close monitoring of ALT and AST levels, as clinically indicated. In addition, if ALT or AST is  $>5 \times \text{ULN}$ , repeat follow-up levels must be obtained within  $7 \pm 2$  days.

If a subject cannot return to the site for liver function testing, a local laboratory may be used. Elevations in LFTs at the local laboratory must be reported immediately to the medical monitor, and the subject must have the tests repeated and sent to the central laboratory as soon as possible (ideally within 48 to 72 hours).

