### 12.3.1 General Considerations

All individual subject data for subjects exposed to study drug will be presented in data listings.

**Continuous variables** will be summarized using the following descriptive summary statistics: the number of subjects (n), mean, SD, median, minimum value (min), and maximum value (max).

**Categorical variables** will be summarized using counts and percentages.

Baseline value, absolute change from baseline, and relative change from baseline will be defined separately for the Ivacaftor Run-in Period and the Active Comparator Treatment Period:

- **Baseline value:**
  - Unless otherwise specified, baseline for the Ivacaftor Run-in Period will be defined as the most recent non-missing measurement (scheduled or unscheduled) collected prior to initial administration of Ivacaftor monotherapy.
  - Unless otherwise specified, the baseline for the Active Comparator Treatment Period will be defined as the most recent non-missing measurement (scheduled or unscheduled) collected prior to initial administration of the VX-661/ivacaftor combination therapy, but no earlier than the measurement at Week -2.
  - For spirometry, the baseline value used for the Active Comparator Treatment Period will be the average of the measurement at Week -2 and the measurement on Day 1 predose. If a subject has an AE leading to an approved extension of the Ivacaftor Run-in Period, and the Week -2 spirometry assessment is between the start and end date (inclusive) of the AE, then the measurement on Day 1 predose will serve as baseline for the Active Comparator Treatment Period.
  - For ECG, the baseline will be defined as the average of the 3 pretreatment measurements at the first day of the corresponding treatment period.
- **Change (absolute change) from baseline** will be calculated as postbaseline value - baseline value.
- **Relative change from baseline** will be calculated as (postbaseline value - baseline value)/baseline value.

The Treatment-emergent (TE) Period will be defined separately for the Ivacaftor Run-in Period and the Active Comparator Treatment Period:

- The TE Period for the Ivacaftor Run-in Period is defined as the first dose in the Ivacaftor Run-in Period to the earlier of the last day prior to the first dose of the Active Comparator Treatment Period or either the Safety Follow-up Visit or 28 days (inclusive) after the last dose for subjects who do not have Safety Follow-up Visit in the Ivacaftor Run-in Period.

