- The TE Period for the Active Comparator Treatment Period is defined as the first dose of the Active Comparator Treatment Period to the Safety Follow-up Visit or 28 days (inclusive) after the last dose for subjects who do not have Safety Follow-up Visit in the Active Comparator Treatment Period.

The TE Period will be used for all safety analyses in the corresponding treatment period.

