##### **13.1.1.3 Documentation of Adverse Events**

All AEs will be collected from the time ICF is signed until the following time points:

- For subjects who do not enroll: until time of screen failure (e.g., screen failure, withdrawal of consent)
- For enrolled subjects who have a Safety Follow-up Visit: through the Safety Follow-up Visit

- For enrolled subjects who do not have a Safety Follow-up Visit: the earliest of
  - 28 days after the last dose of study drug
  - The ETT Visit, if that visit is 3 weeks or later following the last dose of study drug (Section 8.1.5)
  - prior to the first dose of study drug in the extension study

All subjects will be queried, using non-leading questions, about the occurrence of AEs at each study visit. When possible, a constellation of signs and/or symptoms will be identified as 1 overall event or diagnosis. All AEs for enrolled subjects will be recorded in the eCRF and source document. AEs for subjects who are screened but not subsequently enrolled in the study will be recorded only in the subject's source documents. The following data will be documented for each AE:

- Description of the event
- Classification of “serious” or “nonserious”
- Date of first occurrence and date of resolution (if applicable)
- Severity
- Causal relationship to study drug(s)
- Action taken
- Outcome
- Concomitant medication or other treatment given
- Indication of dose limiting toxicity

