8.3 Safety Set

The **Safety Set**, defined separately for the **Ivacaftor Run-in Period** and the **Active Comparator Treatment Period**, includes all subjects who received at least 1 dose of study drug in the corresponding treatment period. The safety analyses will be performed separately for the Ivacaftor Run-in Period and the Active Comparator Treatment Period; subjects will be analyzed according to the treatment they received.

For the safety analysis, the following analyses period will be defined as below:

- The **pre-treatment period (Ivacaftor Run-in Period only)** is defined as the period after the informed consent/assent date and before the initial dosing of study drug in the Ivacaftor Run-in Period.
- The **Treatment-emergent (TE) Period** will be defined separately for the Ivacaftor Run-in Period and the Active Comparator Treatment Period:
 - The TE Period for the Ivacaftor Run-in Period is defined as the date of the first dose in the Ivacaftor Run-in Period to 1) the last day prior to the first dose of the Active Comparator Treatment Period or 2) either the Safety Follow-up Visit or 28 days (inclusive) after the last dose, whichever is earlier, for subjects who discontinue treatment during the Ivacaftor Run-in Period and are not randomized in the Active Comparator Treatment Period.
 - The TE Period for the Active Comparator Treatment Period is defined as the first dose of the Active Comparator Treatment Period to the Safety Follow-up Visit or 28 days (inclusive) after the last dose, whichever is earlier, in the Active Comparator Treatment Period.

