9.4.1 Adverse Events

For analysis purposes, AEs will be classified as pretreatment AEs, TEAEs during the Ivacaftor Run-in Period, TEAEs during the Active Comparator Treatment Period, or post-treatment AEs, defined as follows:

- **Pretreatment AE:** any AE that started before initial dosing of study drug in the Ivacaftor Run-in Period.
- **TEAEs during the Ivacaftor Run-in Period:** any AE that increased in severity or that was newly developed at or after initial dosing of study drug through the end of the TE Period for the Ivacaftor Run-in Period.
- **TEAEs during the Active Comparator Treatment Period:** any AE that increased in severity or that was newly developed at or after initial dosing of study drug through the end of the TE Period for the Active Comparator Treatment Period.
- **Post-treatment AEs:** any AE that increased in severity or that was newly developed beyond the TE Period.

For AEs with a missing or partial start date, if there is no clear evidence that the AEs started (or increased in severity) before or after the first dose date for the Active Comparator Treatment Period, the AE will be considered to be a TEAE for the Active Comparator Treatment Period (see Section 11.7). If there is clear evidence that the AE started before the first dose date for the Active Comparator Treatment Period, but there is no clear evidence

that the AE started before or after the first dose date for the Ivacaftor Run-in Period, the AE will be considered to be a TEAE for the Ivacaftor Run-in Period. Similarly, if there is no clear evidence that the AEs started (or increased in severity) before or after the start of the post-treatment period, the start date will be imputed to be the earliest possible time in the TEAE period and the AE will be considered to be a TEAE.

Unless otherwise stated, all TEAE summaries will be provided separately for the Ivacaftor Run-in Period and the Active Comparator Treatment Period. Presented percentages will be calculated based on the number of subjects in the Safety Set of the corresponding period.

Based on the reported severity and relationship to study drugs, TEAEs can be categorized as follows:

By relationship to the study drugs, treatment emergent adverse events (TEAEs) will be classified into 4 categories:

- Not related
- Unlikely related
- Possibly related
- Related.

By severity, TEAEs will be classified into 4 categories:

- Mild (Grade 1): Mild level of discomfort and does not interfere with regular activities

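### SAP 8.3 ends the treatment-emergent period at day 28 after the last dose even when the Safety Follow-up Visit falls on days 29-35, whereas Protocol 12.3.1 runs it to that visit

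*SAP*

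**What the plan says.** For the Active Comparator Treatment Period, Protocol 12.3.1 runs the TE period from first dose "to the Safety Follow-up Visit or 28 days (inclusive) after the last dose for subjects who do not have Safety Follow-up Visit". The visit sets the end date, and the 28-day limit is a fallback. The run-in definition in the same section has the same structure for subjects who do not go on to randomized dosing: "either the Safety Follow-up Visit or 28 days (inclusive) after the last dose for subjects who do not have Safety Follow-up Visit".

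SAP 8.3 drops the condition. The period runs from "first dose of the Active Comparator Treatment Period to the Safety Follow-up Visit or 28 days (inclusive) after the last dose, whichever is earlier", for every subject. Its run-in definition likewise takes whichever of the visit and 28 days comes first, for subjects who stop in the run-in and are not randomized.

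The Protocol Synopsis (Study Duration) sets the visit window: "A Safety Follow-up Visit will occur 28 days ± 7 days after the final dose of study drug". Protocol 13.1.1.3 sets how long adverse events (AEs) are collected: "For enrolled subjects who have a Safety Follow-up Visit: through the Safety Follow-up Visit".

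SAP 9.1 makes the TE period the default for safety analyses. SAP 9.4.1 classes as post-treatment "any AE that increased in severity or that was newly developed beyond the TE Period".

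**The concern.** The TE period decides which safety data reach the summary tables. Where the SAP's period ends before the visit, AEs collected under the protocol and assessments scheduled at that visit fall outside it. For subjects seen on days 29-35:

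- An AE with a known onset or worsening after day 28 is treatment-emergent under the protocol and post-treatment under the SAP, so it leaves the TEAE tables.
- Protocol 11.7.7 requires liver tests "while subjects are receiving study drug treatment and at the Safety Follow-up Visit". A threshold value first seen there leaves the TE-based counts of potentially clinically significant (PCS) values and the elevated-LFT listing (SAP 9.4.1.5).
- Protocol Table 3-2, footnote j, says: "Single ECGs will be performed at Week 8, ETT, and Safety Follow-up Visits". A PCS ECG value first seen at the follow-up visit leaves the count in SAP 9.4.2.
- Under Protocol 11.7.8, the off-treatment eye examination for subjects under 18 who stop treatment or do not enter the extension may be done at this visit. A cataract first found there leaves the TE cataract summary and listing (SAP 9.4.7).

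The same data can therefore give different safety counts depending on which document the programmer follows. SAP 9.1 adds some uncertainty. It keeps the follow-up visit as a nominal visit for safety parameters but does not say whether that overrides the TE cut-off in by-visit summaries.

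**Working it through.** The plan gives no figure to reproduce. The check applies both rules to every permitted visit day.

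**Inputs.** The visit window is 28 ± 7 days, so days 21 to 35 after the last dose, which is 15 days (Protocol Synopsis, Study Duration). Randomized dosing runs from Day 1 to the evening before the Week 8 Visit (Day 57), so 56 days (Protocol 10.2 and Table 3-2).

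**Rules.** Let s be the visit day, counted from the last dose.

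- Protocol: TE end = s if the visit is held; 28 if it is not.
- SAP: TE end = min(s, 28) if the visit is held; 28 if it is not.

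| Follow-up visit | Protocol end | SAP end | Gap (days) |
|---|---|---|---|
| Not held | 28 | 28 | 0 |
| Days 21 to 28 | s | s | 0 |
| Day 29 | 29 | 28 | 1 |
| Day 32 | 32 | 28 | 4 |
| Day 35 | 35 | 28 | 7 |

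The gap on days 29 to 35 is s − 28, so 1, 2, 3, 4, 5, 6 and 7 days. The rules differ on 7 of the 15 permitted days.

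**Gap as a share of the protocol's TE period**, whose length is 56 + s days for a subject who completes dosing:

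- s = 29: 1/(56 + 29) = 1/85 = 1.2%
- s = 32: 4/(56 + 32) = 4/88 = 4.5%
- s = 35: 7/(56 + 35) = 7/91 = 7.7%

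For subjects who stop during the run-in, the gap is again 1 to 7 days when the visit falls on days 29-35.

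**What cannot be computed.** The documents give no distribution of visit dates within the window, no rate of entry to the extension study (which can remove the need for the visit) and no AE rate. The numbers of shortened TE periods and of reclassified events are therefore unknown.

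**The case against.** The best defence is that the SAP may set this detail. Protocol Section 12 calls itself a summary and leaves the details to the SAP. A 28-day cap is a reasonable choice: it bounds the off-drug window, stops a late visit from extending it, and matches the limit that the protocol already applies to subjects with no follow-up visit. It also gives the post-treatment AE category some content. Under the protocol rule that category is nearly empty for subjects who have the visit, because routine AE collection stops there and only later related SAEs are reported.

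Part of this stands. The cap could be deliberate, and it could be declared in SAP Section 3, which is not visible in the public document (its contents list passes from Section 2 to Section 4). The data are also not lost. They remain in the individual listings (SAP 9.1), the SAE and death listings (9.4.1.4), the out-of-range laboratory listing (9.4.1.5) and the count of cataracts after first dose (9.4.7).

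The argument from uniformity is weak. The SAP rule also stops at the visit when that falls on days 21-27, so the off-drug window still depends on scheduling. The SAP's rule for AEs with unclear start dates, which defaults to treatment-emergent, does not help events with known dates after day 28. No visible text explains the change.

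A reader might infer more: that the SAP hides safety events, that it favours one arm, or that nearly half of subjects are affected because 7 of 15 permitted days fall after day 28. The documents support none of these. The events are listed, and the rule is the same for both arms. The 7 of 15 counts days in the window, not subjects; visits are targeted at day 28.

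**Conclusion.** The two documents contradict each other on when the TE period ends, in both the randomized phase and the run-in. The contradiction affects only subjects whose follow-up visit falls after day 28. For an in-window visit it amounts to 1 to 7 off-drug days, or 1.2% to 7.7% of the protocol's TE period after a full 56 days of dosing.

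The consequence is minor and descriptive. Some dated AEs, and some laboratory, ECG or cataract findings first seen at the visit, move out of the TE-based outputs, although AE collection runs through that visit. SAP 9.4 plans no statistical testing of safety, no between-arm bias is claimed, and the Full Analysis Set and efficacy analyses are unaffected. That the wordings conflict is certain. That the change is undeclared is not, because SAP Section 3 cannot be seen.

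**What to change.** In SAP 8.3, align both TE definitions with Protocol 12.3.1: through the follow-up visit where one is held, and 28 days after the last dose only where none is. State that assessments and eye examinations at that visit count in the TE-based TEAE, PCS, elevated-LFT and cataract outputs, and that the nominal follow-up visit in SAP 9.1 falls within the TE period.

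The cost is SAP wording and one derivation on dates already collected. There are two downsides. TEAE and PCS counts may rise slightly. The off-drug window will also vary with the visit date, up to day 35 and longer for an out-of-window visit.

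If the 28-day cap is deliberate, the SAP should declare it as a departure from the protocol and give the reason, unless Section 3 already does so.

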9 STATISTICAL ANALYSIS

9.1 General Considerations

The Schedule of Assessments is provided in [Appendix C](#). The precision standards for reporting safety and efficacy variables are provided in an internal Biometrics document that specifies the programming rules including the precision for derived variables.

All individual subject data for subjects who were randomized or received at least 1 dose of study drug, i.e., All Subjects Set, will be presented in data listings, with indicator of dosing period, i.e., Ivacaftor Run-in Period vs. Active Comparator Treatment Period, as applicable. Listings related to Active Comparator Treatment Period only will be based on the Active Comparator Subjects Set.

Continuous variables will be summarized using the following descriptive summary statistics: the number of subjects (n), mean, standard deviation (SD), standard error (SE), median, minimum value (min), and maximum value (max).

Categorical variables will be summarized using counts and percentages.

Baseline value, Absolute change from baseline and Relative change from baseline will be defined separately for the Ivacaftor Run-in Period and the Active Comparator Treatment Period:

Baseline value:

- Unless specified otherwise, baseline for the Ivacaftor Run-in Period will be defined as the most recent non-missing measurement (scheduled or unscheduled) collected prior to initial administration of Ivacaftor monotherapy.
- Unless specified otherwise, the baseline for the Active Comparator Treatment Period will be defined as the most recent non-missing measurement (scheduled or unscheduled) collected prior to initial administration of the VX-661/ivacaftor combination therapy or ivacaftor monotherapy (placebo/ivacaftor) during the Active Comparator Treatment Period, but no earlier than the measurement at Week -2.
- For spirometry, the baseline value used for the Active Comparator Treatment Period will be the average of the measurement at Week -2 and the measurement on Day 1 predose. If a subject has an AE leading to an approved extension of the Ivacaftor Run-in Period, and the Week -2 spirometry assessment is between the start and end date (inclusive) of the AE, then the measurement on Day 1 predose will serve as baseline for the Active Comparator Treatment Period.
- For ECG, the baseline will be defined as the average of the non-missing pretreatment measurements (triplicate) on Day 1 (the first day) of the corresponding treatment period.

- For sweat chloride, the baseline value will be the mean of the last values on the left and the right arm prior to the first dose of the study drug of the corresponding treatment period.

Note that references to baseline hereafter should always be interpreted in the context of the corresponding treatment period.

Change (absolute change) from baseline will be calculated as Post-baseline value – Baseline value.

Relative change from baseline will be calculated and expressed in percentage as 100% × (Post-baseline value – Baseline value)/Baseline value.

Treatment-emergent (TE) Period

There are two treatment periods in this study as defined in Section 8.3. The TE periods will be used for safety analyses unless specified otherwise.

Unscheduled visits: Unscheduled visit measurements will be included in analysis as follows:

- In scheduled visit windows per specified visit windowing rules.
- In the derivation of baseline/last on-treatment measurements.
- In the derivation of maximum/minimum on-treatment values and maximum/minimum change from baseline values for safety analyses.
- In individual subject data listings as appropriate.

Visit windowing rules: The analysis visit windows for protocol-defined visits are provided in [Appendix C](#). The windows will be applied using the following rules for both scheduled and unscheduled visits:

1. If no measurement is available within a visit window, the assessment will be considered missing for the visit;
2. If there is more than one measurement available within the same visit window, use the following rules:
 - For all efficacy parameters, if there are multiple measurements within a visit window, the record at the scheduled visit will be used. Otherwise,
 - The record closest to the target day will be used;
 - If there are multiple records with the same distance to the target day, the latest record will be used.
 - Assessments at early treatment termination (ETT) visit will follow the windowing rules for regular visits up to Week 8.
 - Assessments at safety follow-up (SFU) visit will follow the windowing rules for regular visits if they fall within the upper boundary of the window for

Week 8, or remain as SFU if they go beyond the upper boundary of the window for Week 8.

- For all safety parameters, if there are multiple measurements within a visit window, then 1) the record closest to the target day will be used; 2) if there are multiple records within the same distance from the target day, the latest record will be used; or 3) SFU visit will not be windowed; instead, it will be used according to the nominal visit in relevant analyses.

Note, spirometry assessments, BMI, weight, and height will be used for both efficacy and safety purposes. Their measurements will follow the visit windowing rules for efficacy parameters.

Incomplete/missing data will not be imputed, unless specified otherwise.

Outliers: No formal statistical analyses will be performed to detect or remedy the presence of statistical outliers, unless specified otherwise.

Multiplicity: A hierarchical testing procedure will be used to control the Type I error at two-sided $\alpha = 0.05$ among the primary and the key secondary endpoints. The testing hierarchy is as follows:

1. Absolute change in percent predicted FEV₁ from baseline through Week 8
2. Relative change in percent predicted FEV₁ from baseline through Week 8
3. Absolute change in CFQ-R respiratory domain score from baseline through Week 8

